We will utilize connectome-based neurofeedback to assess patterns of functional connectivity within a previously identified “opioid abstinence network”. This network was identified using a whole-brain machine learning approach and predicted subsequent opioid relapse among methadone-maintained individuals. This network was robust, relatively unchanged in follow-up analyses controlling for other clinical variables (e.g., methadone dose, years of opioid use), predicted opioid relapse from different fMRI tasks as well as resting state, and predicted opioid use at multiple time points (two scanning sessions conducted 3 months apart). Design: Individuals on methadone (N=24) will receive active (n=24) connectome-based neurofeedback at 3 weekly scanning sessions (training scans 1-3). Training scans will include both feedback and transfer (i.e. no feedback) runs. Baseline (one week prior to training scan 1) and follow-up (one week following training scan 3) scans will be conducted to test the effects of feedback training on intrinsic connectivity during resting state and fMRI tasks, as in our pilot data. Clinical features of OUD (opioid use, craving, negative affect) will be assessed weekly and at one month follow-up.

Aim 1. To determine if connectome-based neurofeedback is associated with reduced opioid use. Aim 1a. We predict that individuals who receive active feedback will report lower

IRB# 2000025618

levels of opioid use from baseline to follow-up scans. *Aim 1b*. We predict that this reduction will persist over time as assessed at 1-month follow-up.

Aim 2. To determine if connectome-based neurofeedback is associated with changes in intrinsic connectivity. *Aim 2a*. Based on evidence that neurofeedback induces changes in intrinsic connectivity[13], we predict that subjects receiving active feedback will show increased opioid abstinence network connectivity during resting state at follow-up versus baseline scans. *Aim 2b*. We predict that this effect will generalize to increased connectivity during fMRI reward and cognitive tasks at these timepoints.

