
4. **Research Plan:** Summarize the study design and research procedures using non-technical language that can be readily understood by someone outside the discipline. **Be sure to distinguish between standard of care vs. research procedures when applicable, and include any flowcharts of visits specifying their individual times and lengths.** Describe the setting in which the research will take place.

Study design: Participants will receive active ($n=24$) connectome-based feedback at three separate scanning sessions (training scans 1-3). . Training scans will include both neurofeedback and transfer (i.e., no feedback) runs conducted at weekly intervals (**Table 1**).

IRB# 2000025618

Additionally, to test the effects of feedback training on intrinsic

U-Tox	X	X	X	X
TLFB for substance use	X	X	X	X

connectivity, baseline (one week prior to training scan 1) and follow-up (one week following training scan 3) scans will be conducted and will include resting state and reward and cognitive task fMRI runs, to compare networks across brain states as in our prior work[49].

Screening visit: To determine eligibility subjects will first take part in a screening visit involving surveys about their health, smoking, substance use behaviors and attitudes, and the ways in which they view themselves. They will also complete a urine drug test. The screening session will take about 1 and ½ hours. If they are eligible, we will also schedule their MRI appointments during this visit.

Debriefing: At the end of the one month study visit, participants will be fully debriefed by study personnel, who will explain more thoroughly the purpose of the study and answer any questions they may have.

Opioid use: Opioid and other substance use will be monitored weekly at each MRI session from baseline to follow-up using urinalysis and the Timeline Followback (TLFB) [50] method, as in our prior work[10, 48]. Behavioral measures of clinical variables (e.g., pain, other substance use, craving and negative affect) will also be collected.

Imaging Protocol: Scanning will be conducted 2-3 hours following daily methadone on a 3T Siemens Prisma scanner with a 32-channel head coil. A member of the research staff will accompany each subject to the MRRC and stay with them for the duration of the study.

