for 10 seconds. We will use implicit feedback, in which subjects are kept unaware of the purpose of feedback, in order to more confidently attribute changes in behavior to modification of brain network dynamics by minimizing the use of explicit cognitive strategies and instead focusing on targeted neural processing[41]. This also avoids complicated instructions, reducing potential experimenter effects. Implicit feedback has been found to be robust and may be advantageous over explicit feedback[41]. The instructions will be, "Try methods that you have found to help you not use opioids or cope with craving in the past. The main thing is to try different strategies and see what works the best for you." Participants will be debriefed after each scan to ask whether they felt that they could control the feedback, and what strategies they used to try to control the feedback. This approach has been used previously including in our own work. [2-6] Transfer runs will be used to test control of the opioid abstinence network without feedback and will be exactly the same as feedback runs with the exception that a fixation cross will be displayed instead of the feedback bar. Subjects will be shown the same arrow cues and given the same instructions to increase the feedback bar.

Hypothesis testing: Network connectivity strength assessed at each scanning session will be entered into SPSS to test the following Specific Aims:

Aim 1: *To determine if connectome-based neurofeedback is associated with reduced opioid use compared with sham feedback.* H1a. Subjects receiving active versus sham feedback will report lower levels of opioid use from baseline to follow-up scans. H1b. This reduction will persist over time, as indicated by reduced opioid use through 1-mo follow-up.

Approach: Opioid use will be monitored by weekly urinalysis and TLFB across the five weeks from baseline to follow-up scans and measured as % negative urines (H1a); or will be measured using TLFB at 1-mo follow-up with abstinence at 1-mo confirmed by urinalysis (H1b). Medication compliance will be tracked via clinic records. Opioid use will be entered into a linear effects model with the between-subject factor of feedback group (active/sham).

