This protocol presents minimal risks to the subjects and Unanticipated Problems Involving Risks to Subjects or Others (UPIRSOs), including adverse events, are not anticipated. In the unlikely event that such events occur, Reportable Events (which are events that are serious or life-threatening and unanticipated (or anticipated but occurring with a greater frequency than expected) and possibly, probably, or definitely related) or Unanticipated Problems Involving Risks to Subjects or Others that may require a temporary or permanent interruption of study activities will be reported immediately (if possible), followed by a written report within 5 calendar days of the Principal Investigators becoming aware of the event to the IRB (using the appropriate forms from the website) and any appropriate funding and regulatory agencies. The investigators will apprise fellow investigators and study personnel of all UPIRSOs and adverse events that occur during the conduct of this research project through regular study emails or via email as they are reviewed by the principal investigators. The protocol's research monitor(s), study sponsors, funding and regulatory agencies, and regulatory and decision-making bodies will be informed of serious and unanticipated and related adverse events or unanticipated problems involving risks to subjects or others will be reported adverse events within 5 days of the event becoming known to the principal investigator.

13. Statistical Considerations: Describe the statistical analyses that support the study design.

Write here

Our previous neurofeedback work showed that data from 10-20 subjects is adequate for demonstrating significant control of activity in a single brain region[13, 65, 68, 69] and that data from two groups of 10-20 subjects is adequate for detecting group differences in control of activity[13, 68]. Our prior CPM work showed that data from N=10 per group is sufficiently powered

IRB# 2000025618

(>.90) to detect differences in connectome-based networks (noncentrality parameter (δ)=5.36, critical t-value=2.10, df=18, power (1- β)=0.99). Finally, we have established retention rates of >85% over 3-months for fMRI studies with methadone patients[10, 70]. Thus, we are confident that a sample size of N=24 (N=12 per group) is sufficiently powered.

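### The claim that 24 participants (12 per group) are enough rests on one 10-per-group network comparison; it gives no basis for the clinical outcomes and does not fit the design text with all 24 on active feedback

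*Combined protocol and SAP*

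**What the plan says.** Section I, item 13 (Statistical Considerations) offers three supports for the sample size.

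- Earlier neurofeedback studies: 10 to 20 subjects sufficed to show control of a single brain region, and "data from two groups of 10-20 subjects is adequate for detecting group differences in control of activity". No effect size or power is given.
- Earlier connectome-based modelling with 10 per group, said to be powered above 0.90 "to detect differences in connectome-based networks (noncentrality parameter (δ)=5.36, critical t-value=2.10, df=18, power (1- β)=0.99").
- Retention above 85% over three months.

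The conclusion is not limited to any outcome: "Thus, we are confident that a sample size of N=24 (N=12 per group) is sufficiently powered".

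The design text differs. The design summary in Section I, item 1 reads "Individuals on methadone (N=24) will receive active (n=24) connectome-based neurofeedback at 3 weekly scanning sessions", and the study design paragraph of item 4 likewise gives active n=24. A sham group nevertheless remains in the statement of Aim 3 in item 1, in the hypothesis tests of item 4, in the tests listed in item 13, and in the payment text of Section VI, item 2.

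The enrolment target in Section III, item 1 is 24 completers, defined by participation in all scanning sessions. Section III, item 2 expects to scan up to 40 people to reach it.

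**The concern.** Aim 1 is opioid use and Aim 3 is craving and negative affect. A power figure for a difference between brain networks does not carry over to these outcomes without a stated link, and none is given. The protocol's own background (Section I, items 1 and 3) says that earlier real-time fMRI work has seldom turned brain training into clinical benefit.

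The reader sees power values above 0.90 and of 0.99 beside an unrestricted claim. The size of difference those values assume is not shown, nor what was compared, nor whether it was a change over time. A null result on opioid use, craving or affect could then be presented as coming from an adequately powered study.

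The number of arms matters as well. The standardised effect that 24 completers can detect differs by a factor of two between the two designs that the protocol describes.

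**Working it through.** **Inputs.** From item 13: n = 10 per group, noncentrality 5.36, critical t 2.10, df 18, power 0.99, and 12 per group for this study. From items 1 and 4: 24 active. From Section III, item 1: 24 completers of all scans. Alpha is not stated; a critical t of 2.10 on 18 df implies two-sided 0.05 (a one-sided test would give 1.73). The effect sizes below are assumptions, because the protocol states none for these outcomes.

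**1. The plan's own figure.**
- t(0.975, 18) = 2.101, which matches 2.10.
- Power from the noncentral t with noncentrality 5.36 and 18 df is 0.999. The stated 0.99 is consistent with this.
- For two equal groups, noncentrality = d × √(n/2), so d = 5.36/√(10/2) = 5.36/2.236 = 2.40.

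The arithmetic is sound. It describes a network difference of about 2.40 SD.

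**2. Outcomes covered.**

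| Outcome | Effect size, SD or power stated in the protocol |
|---|---|
| Opioid use (Aim 1) | None |
| Network connectivity (Aim 2) | At most the 10-per-group figure; the comparison is not described |
| Craving, negative affect (Aim 3, H3a) | None |
| Correlations (H3b, replication) | None |

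**3. If there are two groups of 12** (df 22, noncentrality = d × √(12/2) = 2.449d; SD is that of the analysed quantity):
- 80% power at d = 1.20, since 2.449 × 1.197 = 2.93 gives power 0.80.
- 90% power at d = 1.39 (1.385 before rounding).
- Power 0.22 at d = 0.5 and 0.47 at d = 0.8.

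The 80% effect is half the d behind the quoted 0.99 (1.20/2.40). For H1a these t-based values are approximate: five urines (baseline, three training scans, follow-up) allow only six values of the percentage negative.

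**4. If there is a single arm of 24** (paired, df 23, noncentrality = d × √24 = 4.899d; d in SDs of the change):
- 80% power at 0.60, since 4.899 × 0.597 = 2.92 gives power 0.80.
- 90% power at 0.69.
- 95% CI half-width = t(0.975, 23)/√24 = 2.069/4.899 = 0.42 SD of the change.

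These values fit the outcomes compared between the baseline and follow-up scans, that is Aim 2 and H3a. They should not be carried to H1b, which "will be measured using TLFB at 1-mo follow-up with abstinence at 1-mo confirmed by urinalysis (H1b"). Table 1 schedules no scan at one month, so 24 scan completers do not guarantee 24 participants at that visit. For illustration, with 20 retained the 80% and 90% values become 0.66 and 0.76.

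**5. Correlations across all 24** (Fisher z, standard error 1/√21 = 0.218):
- 80% power: tanh((1.960 + 0.842)/√21) = tanh(0.611) = 0.55.
- 90% power: tanh((1.960 + 1.282)/√21) = tanh(0.707) = 0.61.

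**The case against.** The strongest reply is that this is a small mechanistic study, described as a first step toward treatment research and funded as an R21, in which formal power for every clinical aim is not expected. That lowers the weight of the point. It does not remove it, because opioid use is Aim 1 and the sufficiency claim has no restriction.

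A second reply is that the mismatch with the single-arm text is only a symptom of the unresolved number of arms. That is partly right: if the sham group stands, the two-sample figure has the correct form. The missing basis for Aims 1 and 3 remains under either design.

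Third, the documents are not wholly silent on brain-behaviour associations. Item 3 reports that network strength predicted abstinence in a separate cocaine sample (n=45, p=0.016). If that was a simple two-sided correlation, which is an assumption, |r| is about 0.36, and power at n=24 would be about 0.40. It concerns cocaine and does not support the claim. Item 13 also points to pilot data in a research strategy that is not part of this document, so one can say only that this protocol states no effect size.

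Attrition is not the weakness: the target is completers, with up to 40 scanned. The analysis set is a separate matter. No passage confines analysis to completers, and the mixed models planned in item 13 can use incomplete data, so the figures above must be labelled as assuming 24 scan completers.

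A reader might infer that the trial is underpowered, or that the 0.99 is miscalculated. The documents support neither. The 0.99 reproduces, and without effect sizes for the clinical outcomes their true power cannot be computed.

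**Conclusion.** The concern holds in this form: the protocol asserts adequate power for 24 participants without showing it. The one quantified support reproduces, depends on an undisclosed difference of about 2.40 SD, bears at most on Aim 2, and has no comparison to apply to if all 24 receive active feedback. What 24 scan completers can detect with 80% power is about 0.60 SD of the change in a single arm, about 1.20 SD between groups of 12, and |r| of about 0.55 for the correlations. These values assume two-sided 0.05, t-based or Fisher z methods, and exactly 24 completers. They do not show that 24 is too few, and they are no argument for a larger study. That a null clinical result would be over-read is a risk created by the wording, not something the documents establish.

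**What to change.** 1. Reconcile the number of arms across Section I, items 1, 4 and 13, and Section VI, item 2.

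2. Replace the blanket sentence in item 13 with the detectable effect for the chosen design at two-sided 0.05, labelled as assuming 24 participants who complete all scanning sessions.
   - **Single arm:** remove the two-sample figure. For Aim 2 and H3a, state 80% power at about 0.60 SD of the change, 90% at about 0.69, and a 95% CI half-width of about 0.42.
   - **Two groups of 12:** limit the 0.99 figure to network outcomes, give its implied d of about 2.40, and say what was compared. State 80% power at a difference of about 1.20 SD of the analysed quantity and 90% at about 1.39, with power 0.22 at 0.5 and 0.47 at 0.8.
   - **Either design:** state that H3b and the replication correlation need |r| of about 0.55 for 80% power, and that no effect-size basis is given for Aim 1. Do not apply the paired n=24 figures to H1b.

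The cost is one rewritten paragraph, once the arm wording has been settled, which is needed in any case. No data, procedure or enrolment is added. The downside is a less favourable stated figure.

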Task fMRI (MIDT, Stroop)	X		X	
Behavioral (craving, affect)	X	X	X	X

Connectome-based predictive

modeling (CPM): We have developed and applied CPM to predict complex behavioral phenotypes in healthy and clinical populations[11, 12, 30, 45-47] including methadone populations[10]. CPM is a data-driven method for generating predictive models of brain-behavior relationships from functional connectivity matrices using cross-validation[11, 30, 31, 45], developed by members of the investigative team (MPI [name]). This approach has been validated in several studies^{e.g.,[11, 30, 45]}. CPM is composed of the following steps: (1) edge selection, in which linear regression is used to relate each edge (correlations between node pairs in the matrix) in the connectome to a behavioral variable of interest (e.g., opioid use) in the training dataset; (2) edge summarization, in which weights of edges identified in Step 1 are summed to create a single summary value for each subject; (3) model building, in which summary scores (the independent variable) are linearly related to the behavioral variable (the dependent variable); (4) model application, in which resultant coefficients from Step 3 are applied to novel connectomes in the testing dataset to generate behavioral predictions; and (5) model evaluation, in which the predictive ability of the CPM is evaluated using either mean squared error or the correlation between predicted and observed behavioral values. Testing models on independent samples ensures that models do not over-fit a specific dataset; rather they generalize and will likely replicate in future work^{e.g.,[11, 30, 45]}. We previously used CPM to predict cocaine abstinence during a 12-week treatment using task data from individuals scanned prior to treatment for cocaine-use[10]. CPM successfully predicted abstinence during treatment (% negative urines) ($p=0.002$). To determine the generalizability of our findings, we tested the ability of the identified networks to predict cocaine-negative urine toxicology outcomes in a separate, heterogeneous sample of cocaine-dependent individuals ($n=45$). Network strength in this independent sample also predicted abstinence during treatment ($p=0.016$)[10]. More recently, we have used CPM to identify a neural network predictive of opioid use among individuals receiving methadone for OUD (Yip et al., In Prep). As with the cocaine network, this network was robust and was not significantly altered in follow-up analyses controlling for other baseline clinical variables including past-month opioid-use or methadone dose. Further consistent with prior CPM work[10, 11, 30, 45], the opioid network was complex and composed of multiple adjacent and nonadjacent nodes with varying degrees of connectivity (i.e., high- versus low-degree nodes). *These data demonstrate the ability of CPM to identify complex neural networks subserving specific addiction outcomes that replicate in independent samples.*

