Aim 2: *To determine if connectome-based neurofeedback is associated with changes in intrinsic connectivity.* H2a. Subjects receiving active versus sham feedback will show increased opioid abstinence network connectivity between resting state acquired at follow-up versus baseline scans. H2b. This effect will generalize to increased connectivity during fMRI reward and cognitive tasks as in our pilot data.

Approach: Opioid abstinence network connectivity strength will be calculated during resting state (H2a), MIDT and Stroop tasks (H2b) as in our pilot data, and will be entered into a linear mixed effects model with the between-subject factor of feedback group (active/sham) and the within-subject factor of time (baseline/follow-up scans).

Aim 3: *To determine if connectome-based neurofeedback is associated with greater improvements in clinical features of OUD than sham feedback.* H3a. Subjects receiving active versus sham feedback will show reduced craving and negative affect at follow-up versus baseline scans. H3b. Increased opioid abstinence network connectivity during transfer runs will be correlated with reduced craving and negative affect.

Approach: Craving (Opioid Craving Scale) and negative affect (Quick Inventory of Depressive Symptomatology) will be calculated at follow-up and baseline scans and compared between groups using repeated measures analysis of variance. Change in opioid abstinence network connectivity strength will be calculated during transfer runs at baseline and follow-up scans. We will test for Pearson's correlations between change in connectivity strength and changes in craving and negative affect.

5. **Genetic Testing** N/A

6. **Subject Population:** Provide a detailed description of the types of human subjects who will be recruited into this study.

IRB# 2000025618

Write here

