The statistical tests will be as follows: Aim 1: Opioid use will be entered into a linear effects model with the between-subject factor of feedback group (active/sham). Aim 2: Opioid abstinence network strength during resting state and task fMRI runs will be compared between time points using linear mixed models with the between-subject factor of group (active/sham) and the within-subject factor of time (baseline/follow-up scan). Aim 3: Craving and negative affect will be compared using linear mixed effects model with the between-subject factor of group (active/sham) and the within-subject factor of time (baseline/follow-up scan). Associations between craving and negative affect and opioid abstinence network connectivity strength during transfer runs will be tested using Pearson's or Spearman's correlations, as appropriate depending on the distribution of the data. Replication: For replication of our pilot data (Figure 2 of research strategy), Pearson's correlations will be tested between opioid abstinence network connectivity strength at baseline and percent opioid-negative urines across the study.

SECTION II: RESEARCH INVOLVING DRUGS, BIOLOGICS, RADIOTRACERS, PLACEBOS AND DEVICES

If this section (or one of its parts, A or B) is not applicable, check off N/A and delete the rest of the section.

A. RADIOTRACERS N/A

B. DRUGS/BIOLOGICS N/A

C. DEVICES N/A

SECTION III: RECRUITMENT/CONSENT AND ASSENT PROCEDURES

1. Targeted Enrollment: Give the number of subjects:

- a. Targeted for enrollment at Yale for this protocol:
24 completers (individuals participating in all scanning sessions).
- b. If this is a multi-site study, give the total number of subjects targeted across all sites: NA

2. Indicate recruitment methods below. Attach copies of any recruitment materials that will be used.

 Flyers	 Internet/web postings	 Radio
 Posters	 Mass email solicitation	 Telephone
 Letter	 Departmental/Center website	 Television
 Medical record review*	 Departmental/Center research boards	 Newspaper
 Departmental/Center newsletters	 Web-based clinical trial registries	 Clinicaltrials.gov

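### Craving and negative affect are scheduled at 1 month, but no planned analysis uses those values; persistence is prespecified only for opioid use (Aim 1b/H1b)

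*Combined protocol and SAP*

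**What the plan says.** **Schedule.** Section I, item 1 (Statement of Purpose, Design) says: "Clinical features of OUD (opioid use, craving, negative affect) will be assessed weekly and at one month follow-up". In Table 1 the row beginning "Behavioral (craving, affect" is marked under Baseline, Training 1-3, Follow-up and 1 mo.

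**Aim 3 analysis.** It is described twice.
- Item 4 (Research Plan, Hypothesis testing) says that the two scales "will be calculated at follow-up and baseline scans and compared between groups using repeated measures analysis of variance".
- Item 13 (Statistical Considerations) says "Craving and negative affect will be compared using linear mixed effects model with the between-subject factor of group (active/sham", and gives the within-subject time factor two levels, baseline and follow-up scan.

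**Aim 3 hypothesis.** H3a in item 4 reads: "Subjects receiving active versus sham feedback will show reduced craving and negative affect at follow-up versus baseline scans".

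**Timing of the later scan.** Item 1 places it one week after the last training session: "follow-up (one week following training scan 3) scans will be conducted to test the effects of feedback training on intrinsic connectivity".

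**Persistence.** For opioid use, H1b states: "This reduction will persist over time, as indicated by reduced opioid use through 1-mo follow-up". The outcome is to be "measured using TLFB at 1-mo follow-up with abstinence at 1-mo confirmed by urinalysis (H1b"). Neither section has a counterpart for craving or negative affect.

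**The concern.** Outcome data are collected at a visit for which the plan gives them no use. The plan treats durability as a question worth asking of opioid use. It lists craving and negative affect beside opioid use as clinical features and measures all three at the same 1-month visit, yet only opioid use has a planned 1-month result.

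Two things are at stake. First, Aim 3 is framed as improvement in clinical features of OUD, but for these two scales the planned evidence is one assessment a week after training ends. If opioid use were still down at 1 month while craving had returned, no planned result would show it. Second, if someone examines the 1-month values later, the contrast and the way it is reported would be chosen after the data were seen. Stating the contrast now avoids that.

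**Working it through.** **1. Schedule against analysis.**

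| Visit | Craving and affect scheduled (item 1, Table 1) | Used in Aim 3 comparison (items 4 and 13) |
|---|---|---|
| Baseline scan | yes | yes |
| Training scans 1, 2, 3 | yes (three visits) | no |
| Follow-up scan | yes | yes |
| 1 month | yes | no |

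Six visits are scheduled and two are used. H3b does not fill the gap: item 4 takes the connectivity change between the baseline and follow-up scans, and Table 1 shows no imaging at 1 month. The point is settled by this comparison. The figures below only indicate what a 1-month estimate could deliver.

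**2. The plan's own power figure.** Item 13 gives noncentrality 5.36, critical t 2.10, df 18 and power 0.99, for 10 per group.
- Implied effect: d = 5.36/√(10/2) = 2.40.
- Two-sided 5% critical value on 18 df: 2.101.
- Power = 1 − F(2.101; df 18, noncentrality 5.36) = 0.999, where F is the noncentral t distribution function.

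The figure reproduces, but it concerns connectome-based networks. The documents give no power, SD or expected effect for craving or negative affect at any visit, so what follows is in SD units.

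**3. Precision of a 1-month change.** Assumption: a single arm, with each participant's 1-month value compared with his or her own baseline. The 95% CI half-width, in SDs of the change score, is t(0.975, n−1)/√n.
- n = 24: 2.069/4.899 = 0.42.
- n = 20: 2.093/4.472 = 0.47.

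The value 20 is an assumption. It is close to 85% of 24 (0.85 × 24 = 20.4), after the retention rate of more than 85% over 3 months cited in item 13. It matters because Section III, item 1 defines the 24 completers by attendance at all scanning sessions, and the 1-month visit has no scan.

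**4. Detectable change, for orientation.** Two-sided 5%, 80% power, noncentral t.
- Single arm, paired: 0.60 SD of the change score with 24, 0.66 with 20.
- Two groups, as items 4 and 13 are worded: d = 1.20 with 12 per group, 1.32 with 10 per group.

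The single-arm and two-group figures answer different questions and are not interchangeable.

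**The case against.** The strongest reply is that the plan is consistent with itself. H3a is expressly about follow-up versus baseline, and a two-level time factor is the model for that hypothesis. Aim 3 makes no persistence claim, and a result reported as planned carries its own time point. This stands: the gap is an omitted analysis of scheduled data, not a model that fails its hypothesis.

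The restriction may also have a design reason. With no scan at 1 month, using the two scan visits keeps H3a aligned with H3b. That is plausible but inferred, since the documents do not say so, and it does not prevent a secondary 1-month estimate. Other scheduled measures, such as withdrawal, impulsivity and the training-visit craving scores, also lack a named test. The 1-month visit differs in that the plan itself poses the durability question there, for opioid use.

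Three stronger readings are tempting and are not supported.
- *That the trial cannot say whether any clinical improvement lasts.* H1b addresses opioid use at 1 month, and item 1 counts opioid use as a clinical feature of OUD. The 1-month craving and affect values will also exist.
- *That a 1-month contrast would show a lasting effect of feedback.* Items 1 and 4 give active feedback to all 24 participants. Without a control, a change mixes any effect of feedback with time in methadone treatment and regression to the mean.
- *That the 1-month estimate has the same precision as the H3a contrast as worded.* That contrast is active versus sham. The 0.42 SD figure assumes one arm and nobody lost between the last scan and 1 month.

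**Conclusion.** The point holds in a limited form. Craving and negative affect are measured at 1 month, both descriptions of the Aim 3 analysis stop at the follow-up scan, and no other analysis takes the 1-month values up. Persistence is prespecified for opioid use alone. Nothing planned is invalidated, and H3a stands as written. This is an inexpensive improvement that widens what the trial can report.

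The size of the benefit is modest: a 1-month change known to within about 0.42 SD of the change score with 24 analysed, or 0.47 SD with 20. These figures assume a single-arm paired comparison, and the number available at 1 month is not fixed by the documents. The schedule comparison itself rests on no assumption.

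**What to change.** In Section I, items 4 and 13:

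1. Name one method for the Aim 3 comparison. Item 4 now specifies repeated measures analysis of variance and item 13 a linear mixed model. Use the linear mixed model in both; it can retain participants who miss the 1-month visit.
2. Fit it without the active/sham term, which cannot be estimated when all 24 participants receive active feedback, and reword H3a to match, as Aim 3a in item 1 already is.
3. Give time three levels: baseline, follow-up scan and 1 month.
4. Keep follow-up versus baseline as H3a. From the same model report the 1-month versus baseline and 1-month versus follow-up changes with 95% CIs, as secondary estimates and not as further significance tests.
5. Describe these as within-person change over time, not as a controlled effect of feedback, and report the number of participants with 1-month values.

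The cost is a short edit in two sections that already need reconciling, and one or two more estimates per scale. No visit, measure or participant is added.
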